### Outcome Analysis Plan

The trial is intended to evaluate the following hypotheses:

**H1:** First-time DWI offenders in the intervention group (*B-SMART mobile web app*) will have significantly fewer IID lockout events than participants in the control group (UC information condition).

**H2:** Lower rates of IID lockout events will be mediated by improvements in Family Functioning, Family Communication, and Shared Positive Family Events in the intervention (*B-SMART mobile web app*) condition compared to the UC information condition.

We will also analyze the moderation of the effect of *B-SMART* by demographics and mediation of IID lockout events by *B-SMART* use in the intervention group.

Three levels of analysis are planned: (1) hypothesis testing using Poisson regression testing the differences in lockout events between the two intervention groups, (2) analysis of possible covariates (e.g., sex, ethnicity, and age of DWI offenders and CFMs), added to the Poisson regression and (3) other exploratory analyses.

**Preliminary Analysis of Baseline Data.** Descriptive data at baseline, with comparisons by treatment group, will be examined to check distributional characteristics and assess any concerns for imbalances that might be considered as covariates in analyses. The potential meaning of non-normality will be examined, i.e., excessive skewness potentially identifying key subgroups. These analyses will be at the level of the individual DWI offenders and CFMs responses and be conducted within 3 months of completion of recruitment. If there is excessive skewness on the IID lockout rates, negative binomial regression will be used.

**Planned Analysis for Hypothesis 1.** The second major analysis will focus on impact of the *B-SMART mobile web app* on primary (IID lockout events) and secondary (DWI offender's alcohol consumption) outcomes and be completed within 1 month of the end of the posttest data collection in Year 2. The effect of *B-SMART* on IID lockout events in Hypothesis 1 will be tested primarily using PROC GENMOD with a Poisson link via SAS Version 9.4, which includes capabilities to test these Poisson models with missing data, account for the temporal design, and include information by participant. Participants will be treated as a random effect and treatment as a fixed effect, at  $p=0.05$  (2-sided). Analyses of primary outcomes will not be released before completion of the intervention. Since CFM and DWI offender can be clustered within the same family, hierarchical models with participants nested within families will be considered.

The secondary outcome of quantity and frequency of alcohol consumption by DWI offenders will be compared in several ways. Quantity and frequency will be evaluated using Poisson models, as well as a composite variable based on total alcohol consumption (the product of the two variables), using negative binomial regression models, unless a Poisson model is sufficient.

Since date of IID lockout events will be collected and alcohol consumption is measured at all three assessments, we will examine the time by treatment interaction in the analyses of Hypothesis 1 to assess the

question of the durability of the effects of B-SMART over time. For example, we will evaluate time to first lockout using a Kaplan Meier approach and the times to subsequent lockouts.

**Mediation Analysis for Hypothesis 2.** To address the predicted mediation effects of family function on improving the effect of the *B-SMART mobile web app* in Hypothesis 2, we will assess a formal effect on predicting fewer IID lockout events. Mediation will be tested by applying regression techniques from Judd and Kenny and elaborated by MacKinnon, with significance of mediation determined via interval estimation using bootstrapping. Ratio of indirect to total effects will estimate the proportion of the effect mediated. The primary mediational analysis will rely on temporal order of the posttests by examining the effect of *B-SMART* on change in the mediators from baseline to 3-month follow-up and in turn their association with changes in the IID lockout events from baseline to the 9-month follow-up and from 3- to 9-month follow-up.

**Ancillary Analysis of Moderators.** Potential moderators (see 3C.7.3) will be tested at  $p=.05$  (2-tailed) unadjusted for multiple tests. For Hypothesis 1, they will be added as interactions by condition in a manner similar to regression testing for effect modification. Gender is included to probe differences by sex of student and employee. For Hypothesis 2, we will explore if improvements in IID lockout events produced by increases in family function by different participant groups (gender, ethnicity, etc.), using moderated mediational analyses. Moderation effects must be large to be detected, so these are ancillary tests.

**Ancillary Analysis of the *B-SMART Mobile Web App* Exposure.** The same mediational analysis techniques described in 3C.8.4 will be used to explore the relationship of exposure to the *B-SMART mobile web app* and pre-post changes in IID lockout events. Summed scores on exposure will be calculated from the SQL database (e.g., time on app, number of visits to the app, etc.) to assess intervention exposure.

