## 3C.7. Outcome Measures

**3C.7.1. Measure of Primary Outcome Variable: IID Lockout Events.** The primary outcome

measure will be frequency of IID lockout events from baseline to 9-month follow-up post-randomization, collected from the Santa Fe DWI program database for each first-time DWI offender participant. Marques, Voas and colleagues have demonstrated in a series of investigations that frequency of lockout events strongly predicts DWI recidivism over time, and as such, IID lockout events are an important and useful proxy measure for DWI recidivism. Given the length of time necessary to accumulate DWI recidivism data (average length of time varies across locales and can be between 2 and 8 years), IID lockout events provide a direct and accessible measure of DWI recidivism within the two-year project timeline.

**3C.7.2. Measures of Secondary Outcome Variables and Mediators.** Alcohol use by the DWI offender, a secondary outcome, will be assessed at baseline, 3-month follow-up, and 9-month follow-up with versions of the Form 90 adapted for online assessment for the CFMs (Form 90-ACS) and first-time DWI offenders (Form 90-AF). The Form 90 measures produce detailed quantity and frequency measure of alcohol use for the first-time offender that are validated by the CFM reports. Family functioning will be assessed at baseline, 3-month follow-up, and 9-month follow-up, as potential mediators of *B-SMART* effects, with DWI offenders and CFMs with three measures: (1) Family Environment Scale – Cohesion and Conflict subscales assesses offender and CFM perceptions of positive and negative family functioning; the two subscales selected are strongly associated with treatment outcome; (2) Family Communication Scale from FACES-IV assesses perception of quality of communication in the family; (3) Pleasant Events Schedule (adapted) assesses shared positive activities within a family. These three measures are also being used in the B-FIT study, allowing for comparison of outcomes across the two studies.

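### The primary lockout test adjusts for no baseline covariate; adding baseline Form 90 drinking, already collected, would be a nearly free but conditional gain in precision

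*Combined protocol and SAP*

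**What the plan says.** The analysis scheme appears in essentially the same words in 3C.8, in Statistical Design and Power (4.4) and in the SAP's Outcome Analysis Plan. Level 1, the test of H1, is "hypothesis testing using Poisson regression testing the differences in lockout events between the two intervention groups". The only model terms stated for it are these: "Participants will be treated as a random effect and treatment as a fixed effect". Level 2 is "analysis of possible covariates (e.g., sex, ethnicity, and age of DWI offenders and CFMs), added to the Poisson regression". A second route to covariates is the baseline comparison, which is to "assess any concerns for imbalances that might be considered as covariates in analyses" and to "be conducted within 3 months of completion of recruitment". No section names baseline drinking as a covariate for lockouts.

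Baseline drinking will nevertheless be on file. Section 3C.7.2 states: "Alcohol use by the DWI offender, a secondary outcome, will be assessed at baseline, 3-month follow-up, and 9-month follow-up". The Form 90 is described there as giving a "detailed quantity and frequency measure of alcohol use for the first-time offender that are validated by the CFM reports". Section 3C.6.1 places randomization after the baseline assessment, and the recruitment and retention plan (2.5) has 300 offenders completing baseline before being randomized, so few values should be missing. Lockout data are obtained only at the 9-month point, so no pre-randomization lockout count is planned.

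**The concern.** The plan itself allows for offenders differing in their lockout rates, through the participant random effect and the negative binomial fallback. Where such differences exist, a baseline variable that predicts them removes part of the variance of the treatment effect. Of the listed baseline measures, offender drinking is the obvious candidate.

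Neither existing route puts it in the primary test. Level 2 is a later step with demographic examples. Screening for imbalance picks variables that happen to differ between arms, which need not be the ones that predict lockouts.

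Only precision is at stake. Buying it by recruitment would be hard if much were needed: the trial wants 300 offenders in months 6-11, and 3C.3 reports 360 first-time offenders in the county in 2015 and 313 first-time convictions in 2016.

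**Working it through.** **Inputs from the documents.** Two-sided 0.05; 90% power; 4 lockouts per 9 months in the control arm; 20% reduction (3.2 lockouts) as the effect that sets the sample size; 119 per group; 15% attrition; 150 randomized per arm. Completers: 255/2, or about 127 per arm.

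**Inputs assumed.** k is the between-offender variance of the lockout rate, relative to a mean of 1. R² is the share of the between-offender log-rate variance explained by baseline drinking. Neither is in the documents, so both are shown as ranges.

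**1. The plan's own figures.** For two Poisson means, n = (1.960 + 1.282)² × (L1 + L2)/(L1 − L2)².
- 4 v 2.4: 10.507 × 6.4/2.56 = 26.3, so 27.
- 4 v 3.2: 10.507 × 7.2/0.64 = 118.2, so 119.

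Both stated figures reproduce. Attrition gives 119/0.85 = 140, and 150 covers it. This sizing sets k = 0.

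**2. Where a gain can come from.** Approximately, Var(log rate ratio) = (1/L1 + 1/L2 + 2k)/n, and adjustment replaces k by k(1 − R²). With k = 0 there is nothing to explain. With k = 0.5 and n = 127:
- Unadjusted: (0.25 + 0.3125 + 1)/127 = 0.0123.
- R² = 30%: (0.5625 + 0.70)/127 = 0.0099, a fall of 19%.

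This formula is somewhat optimistic for Poisson regression with robust standard errors, so simulation is used for the size.

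**3. Simulation.** 10,000 trials per setting, 127 per arm, 4 v 3.2 lockouts, log-normal offender rates, Poisson regression with robust standard errors. The last column is 127/ratio − 127.

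| k | R² | Variance ratio, adjusted/unadjusted | Power, unadjusted → adjusted (%) | Equivalent extra offenders per arm |
|---|---|---|---|---|
| 0.25 | 10% | 0.956 | 69.2 → 70.4 | 6 |
| 0.25 | 30% | 0.874 | 69.2 → 74.9 | 18 |
| 0.25 | 50% | 0.782 | 69.1 → 79.5 | 35 |
| 0.5 | 10% | 0.950 | 52.2 → 54.3 | 7 |
| 0.5 | 30% | 0.837 | 52.8 → 60.4 | 25 |
| 0.5 | 50% | 0.726 | 53.3 → 67.0 | 48 |
| 1 | 10% | 0.949 | 37.5 → 39.1 | 7 |
| 1 | 30% | 0.820 | 36.5 → 42.9 | 28 |
| 1 | 50% | 0.680 | 36.5 → 50.0 | 60 |

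At R² = 5% the variance falls by about 2% and power rises by at most 1 point. If all 150 per arm have program records, power at k = 0.5 goes from about 60% to 62%, 67% and 74-75% at R² = 10%, 30% and 50%.

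**4. When a condition fails.** At R² = 0 the variance ratio is 1.004 to 1.006, and power changes by −0.1 to −0.3 points. At k = 0 power is 91.9% unadjusted and 91.8% adjusted.

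**5. Dependence on the variance model.** The gain appears in the reported standard error only if the model allows for heterogeneity. In a separate run at k = 0.5 and R² = 30%, the true standard deviation of the log rate ratio was 0.111 unadjusted and 0.101 adjusted, but the plain Poisson standard error was 0.067 in both. Adjusted plain Poisson had type I error of 12-16% at k = 0.25 and 28-38% at k = 1. With robust standard errors the adjusted test ran at 5.2-6.4%, slightly liberal, and in a direct comparison it was no worse than the unadjusted test (5.9% against 6.0-6.1%). A negative binomial check (3,500 trials) gave power gains of 1-2, 6-7 and 11-14 points at R² = 10%, 30% and 50%.

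**The case against.** The other side has real force on size.
- Under the plan's own sizing assumption the gain is nil.
- No section shows that baseline drinking predicts lockouts; 3C.7.1 says only that lockouts predict recidivism. R² of 30% or 50% needs a correlation of 0.55 or 0.71 (the square roots) between one self-report and the underlying log lockout rate.
- R² may well be low. A lockout requires an attempt to start the car with alcohol present, and the covariate is online self-report by people on probation.
- At R² = 10% the gain is worth 6-7 offenders per arm, less than the margin of 150 − 140 = 10 already in the plan.
- The simulation enters the covariate in exactly its correct form. Assuming instead that 40% of offenders report no drinking, with R² then referring to latent drinking, the variance falls by 3-4%, 10-15% and 19-27% at R² = 10%, 30% and 50%.

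All of this stands, and it is why the tabulated gains are upper-end.

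It can also be said that level 2 is an open list and that the Analysis Subcommittee has still to write a detailed analysis plan, so baseline drinking is not excluded. That is true, but the primary test remains unadjusted unless the term is named there.

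A reader might infer that covariates could be picked after outcomes are seen. The timetable for the baseline check does not support that. Recruitment ends in month 11, so the check is due by month 14. The first 9-month records fall at about month 6 + 9 = 15.

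**Conclusion.** The point holds as an efficiency refinement. The primary H1 test omits a pre-randomization measure that is already collected and closely related to the outcome, and including it has almost no downside. Under assumed k of 0.25 to 1, and allowing for simulation error, the variance of the log rate ratio falls by about 4-5%, 12-19% and 21-33% at R² = 10%, 30% and 50%. Self-report error, zeros and a wrong functional form would all reduce these figures. The true size is unknown and may be as small as 1-2 power points.

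Two stronger readings are tempting and are not supported. One is that omitting the covariate biases the unadjusted comparison. It does not: randomization protects the comparison, and with a log link both models target essentially the same rate ratio. The other is that the low starting powers in the table come from the missing covariate. They come from overdispersion, which adjustment does not replace handling.

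**What to change.** In 3C.8.2, 4.4 and the SAP, add one term to the primary H1 count model. Suggested wording:

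> The primary H1 model includes, in addition to treatment, log(1 + offender-reported baseline Form 90 total consumption), where total consumption is quantity times frequency in [units] over [recall window]. The term is included whatever the baseline balance. A missing value is replaced by the mean over both arms combined. The unadjusted model is reported as a sensitivity analysis.

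The units and recall window must be filled in before outcome data are seen. No section states them, and log(1 + x) depends on the units. Offender report is the natural source, because offender consumption is the secondary outcome and the family member's report serves to validate it.

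The term goes into whichever overdispersion-allowing model the plan uses: participant random effect, negative binomial or robust standard errors. That choice is a separate matter, and this change need not alter it. Demographic covariates can stay at level 2.

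The cost is one extra parameter and a few lines of text in three places, including one line to define the covariate. No new data are needed.

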### 3C.6. Randomized Trial Evaluating *B-SMART* (Specific Aim 4; Months 8-24)

**3C.6.1. Experimental Design.** The *B-SMART mobile web app* will be evaluated in a randomized pretest-posttest controlled design. In months 6-11, first time DWI offenders and CFMs will be recruited for participation in the trial. First-time DWI offenders and their CFMs will be randomized together to the intervention (*B-SMART*)

(n=150) or a usual and customary (UC) IID information condition comparison group (n=150) following baseline assessment. Assessment via web-based surveys will be conducted with the DWI offenders and CFMs at baseline, 3-month follow-up, and 9-month follow-up

post randomization. Also, information on frequency of alcohol-positive IID tests (termed “lockout events”) will be acquired by the project from the Santa Fe County and Municipal DWI Program at the 9-month assessment point (posttest only) for each DWI offender. Thus, the proposed efficacy trial (see **Figure 5**) will be a 2 (level of treatment – app intervention vs. UC information) x 3 (level of time – baseline vs. 3-month follow-up vs. 9-month follow-up) mixed factorial design. Baseline and follow-up data collection will be conducted via online surveys and a customized web portal and include DWI offender and CFM alcohol frequency and use measures and measures of family communication and functioning (see 3C.7). Participants will fill out a locator form with contact information and collateral contact information to locate them for assessment at the 3-month and 9-month follow-ups. We have employed these locator procedures in prior trials, keeping average loss across 9 months at 15%-20%. Cumulative IID lockout event data will be collected for all DWI offenders from the Santa Fe County DWI Program at the 9-month assessment point.

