### **3.2. ADEQUACY OF PROTECTION AGAINST RISKS**

#### **3.2.A. Informed Consent and Assent.**

Human Subjects oversight will be conducted by the Western Institutional Review Board (WIRB; DHHS IRB Reg. No. IRBooooo53; FWA No. 00003715) and the University of New Mexico's Institutional Review Board (DHHS IRB Reg. No. IRBoooo431; FWA No. 00004690). All consenting procedures will be IRB-approved. The IRB(s) will review and approve subject materials (including recruitment letters, consent forms, survey instruments) and data management procedures prior to study implementation. Potential participants will be informed of the study purposes and procedures, given opportunities to ask questions and have them answered, and provide informed consent according to IRB-approved guidelines.

Focus group and usability test participants will be consented in-person and will sign an IRB-approved consent form. For the randomized trial, DWI offenders recruited to the study will be consented in-person and will be administered by a UNM Project Coordinator. Project staff will provide participants with copies of their signed IRB-approved consent forms. For the randomized trial, CFMs will be consented online and will have an option to save or print the IRB-approved consent. Participants will only be enrolled in the trial if both the DWI offender and CFM consent to participate. Consent forms will be either Spanish or English, dependent on the participants' language.

The IRB-approved consent forms will describe the purpose of the project, risks and benefits, and selection criteria. Participation will be voluntary, with the right to stop participating at any time. No clinical data will be captured. All data coding, data entry, analysis, and reporting activities will be conducted by KB. Participants will be informed that they have a right to withdraw from the study at any time. No additional data will be collected from participants who decide to withdraw; however, the information collected prior to withdrawal will remain in the study. IRB-approved surveys and discussions will be carried out under the supervision of senior project staff.

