### **3.3. DATA AND SAFETY MONITORING PLAN**

A data safety and monitoring plan will be implemented for this project, following well-established procedures within KB and UNM. We will not set up an independent Data Safety and Monitoring Board because this trial is very low risk; does not include use of therapeutics; and physical risks are not anticipated. The progress of the research will be monitored monthly by the PI, Co-Investigators, Project Coordinator, and Project Biostatistician, who will meet bi-weekly to discuss the activities in the project, participant recruitment, and data collection. Any issues that the research scientist has identified will also be discussed at that time.

The study investigators have extensive experience in clinical trials organization and management, including data safety monitoring for single site and multisite trials. Relevant study staff will also be trained in monitoring and documenting adverse events.

Critical events will be reviewed by the investigators to ensure that project methods have not been intrusive or disruptive. Annual reports on data safety and monitoring are submitted to the IRBs. Compliance with data collection protocols will be monitored throughout data collection by the Investigators and Project Coordinator. The data management staff at KB will examine the quality of data input throughout the data collection period following standard quality control and assurance procedures (e.g., double entry of hard-copy coded data; detection and estimates of keystroke errors, identification of systematic mistakes in coding or responses; range checks). Analyses of the data will be performed by [name] and [name] at the conclusion of the data collection period to assess distributional assumptions and the success of randomization. By having the Project Coordinator, Project Biostatistician and data management staff monitor the data, the PI's conflict of interest is reduced. The PI and Project Coordinator are responsible for reporting all adverse events to the IRBs. Only Grade 1 events are expected on this trial. Thus, adverse events will be reported annually, as required by DHHS. This report will be reviewed by the IRBs. Any action taken by the IRB or project investigators resulting in a temporary or permanent suspension of the trial will be communicated immediately by the PI to the NIH program officer.

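### The model that decides H1 is not fixed: the switch from Poisson to negative binomial has no criterion, and the participant random effect that could cover overdispersion is not defined

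*Combined protocol and SAP*

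**What the plan says.** The H1 test "will be tested primarily using PROC GENMOD with a Poisson link via SAS Version 9.4" (SAP, Outcome Analysis Plan, Planned Analysis for Hypothesis 1; repeated in protocol 3C.8.2 and attachment 4.4). The same paragraph says that the procedure can "account for the temporal design, and include information by participant", and adds: "Participants will be treated as a random effect and treatment as a fixed effect". That is all the text gives on the participant random effect, apart from a remark that family-nested models will be considered.

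The route to another model stands in the paragraph on preliminary analysis of baseline data (SAP; 3C.8.1; 4.4): "If there is excessive skewness on the IID lockout rates, negative binomial regression will be used". The other mention of negative binomial concerns the alcohol composite, not lockouts. No dispersion check, scale parameter or robust variance appears for H1.

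Three other places bear on this:
- The Data and Safety Monitoring Plan (3.3) schedules analyses "at the conclusion of the data collection period to assess distributional assumptions and the success of randomization", with no lockout criterion.
- On data structure, 3C.6.1 says: "Cumulative IID lockout event data will be collected for all DWI offenders". The SAP says: "Since date of IID lockout events will be collected".
- The sample size (3C.6.5, 4.4, SAP) assumes Poisson counts throughout.

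**The concern.** A Poisson model takes the variance of the counts to equal their mean. If some offenders trigger many lockouts and most trigger few, the variance exceeds the mean, Poisson standard errors are too small, and the H1 p-value and interval are too optimistic.

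The plan foresees a poor Poisson fit, but it leaves two decisions to the analyst: what degree of skewness is excessive, and what the random effect means in practice. With one total per offender, it could be a random intercept or be left out. With dated events, it could be a repeated-interval model. In PROC GENMOD, a GLM and GEE procedure, the analyst could run an ordinary GLM, run a GEE, or move to another procedure. Two competent analysts could therefore get different p-values for the single primary test from the same data.

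**Working it through.** **Inputs from the plan.** Control mean 4 lockouts over 9 months; reductions of 40% and about 20%; two-sided 5%; 90% power; 27 and 119 per group; 150 randomized per arm; 15% attrition (all in Sample Size Determination). 150 × 0.85 = 127.5, so 127 per arm is used.

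**The plan's own figures.** With n = (1.960 + 1.282)² × (1/m₁ + 1/m₂) / ln(m₁/m₂)²:
- 4 v 2.4: 10.507 × 0.6667 / 0.2609 = 26.8, so 27.
- 4 v 3.2: 10.507 × 0.5625 / 0.0498 = 118.7, so 119.

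Both reproduce, with no allowance for overdispersion.

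**Assumption.** Variance = mean + k × mean², with k = 0.1, 0.25, 0.5 and 1. At mean 4, variance/mean = 1 + 4k = 1.4, 2, 3 and 5.

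**Ordinary Poisson, no switch.** Type I error is 2 × [1 − Φ(1.96/√(1 + 4k))]. At k = 0.5, 1.96/√3 = 1.13, giving 0.258. The four values are 0.098, 0.166, 0.258 and 0.381. Simulation (gamma-Poisson, 20,000 trials) agrees within about 1 point.

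**Models that allow for overdispersion.** Poisson with robust variance gives 5.0-5.6% throughout. A random-intercept Poisson fitted by maximum likelihood gives 4.9%, 5.0% and 5.1% at variance/mean 2, 3 and 5 (1,000 trials each).

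**The switch, on pooled final counts.** The cut-offs are assumed, because the plan has none. A Poisson count has skewness 1/√mean, which is 0.5 at mean 4, so 0.5 is a natural reference. A robust test is taken when the switch fires.

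| Type I error at variance/mean | 1.4 | 2 | 3 | 5 |
|---|---|---|---|---|
| cut-off 0.5 | 5-6% | 5% | 5-6% | 5% |
| cut-off 1 | 9% | 10% | 6% | 5-6% |
| cut-off 2 | 10% | 16% | 24-25% | 26% |

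**Shape.** Variance/mean is now held at 3, with a given share of high-rate offenders. Ordinary Poisson error is about 25-26% in every column.

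| High-rate share | 10% | 20% | 30% | 50% |
|---|---|---|---|---|
| median skewness | 2.08 | 1.47 | 1.13 | 0.66 |
| cut-off 1 fires | 100% | 100% | 83% | 1% |
| error, cut-off 0.5 | 5% | 5% | 5% | 7% |
| error, cut-off 1 | 5% | 5% | 9% | 25-26% |
| error, cut-off 2 | 12% | 26% | 26% | 25-26% |

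The same overdispersion can thus give very different skewness. If the plan's negative binomial model replaces the robust test on switching, error in these mixtures when it fires is about 3% to 8% rather than a steady 5%. The high end is the 10% mixture and the low end the 50:50 split.

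**Power for a 20% reduction.** Φ(0.2231/√((0.5625 + 2k)/n) − 1.96). At k = 0.5 and n = 127, 0.2231/0.1109 − 1.96 = 0.05, giving 52%. At variance/mean 1, 1.4, 2, 3 and 5:
- n = 127: 92%, 82%, 68%, 52% and 35%.
- n = 150: 95%, 88%, 76%, 59% and 40%.
- n per arm for 90%: 119, 161, 225, 330 and 541.

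**The case against.** The strongest reply is that the SAP does name a participant random effect, so an ordinary Poisson fit would ignore its text, and a random effect holds error near 5%. That stands as far as it goes. A reader might infer that the trial will run its primary test at 25% or 38% error; the documents do not support that. They give no dispersion figure, and the inflation needs two things at once: the random effect is not effectively fitted, and the switch does not fire. What the reply does not supply is a record structure, an estimation method or a procedure that clearly fits the model.

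Second, a reader might infer that skewness cannot detect the problem. That is too strong. At a cut-off of 0.5, error was about 5-7% in every case tested, including the 50:50 split, which is an unfavourable case and not a typical one. But the plan states no cut-off, and 0.5 is the Poisson value only at mean 4. It would be 1.0 at mean 1, and with no overdispersion at mean 4 a cut-off of 0.5 still fires in 44% of trials.

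Third, because the switch sentence sits in a paragraph of analyses due within 3 months of completing recruitment, a reader might infer that the model must be chosen before the 9-month lockout data arrive. The sentence has no date of its own, and the check at the end of data collection in section 3.3 is compatible with applying it then. The two places need reconciling, but they do not contradict each other.

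Finally, the study-team section promises a fuller analysis plan. It may be meant to settle this, but no criterion is visible in the documents.

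**Conclusion.** The point holds as a gap in pre-specification of the primary test and should be closed before lockout data are analysed. The switch has no statistic or cut-off, its gauge is indirect, and the random effect that could make it unnecessary is named only. Depending on how those sentences are read, type I error under the assumed variance/mean of 1.4 to 5 runs from about 5% (robust variance or fitted random effect) to about 10-38% (ordinary Poisson, no switch). With a switch on gamma-Poisson counts it is about 5-6%, 5-10% or 10-26% at cut-offs 0.5, 1 and 2.

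These figures rest on assumed dispersion and shape, mean 4 and 127 per arm. Those for ordinary Poisson and for cut-offs 1 and 2 were also run at 150 per arm and moved by at most about 1 point. The random-effect result was checked only for gamma-Poisson counts. The figures do not show that the plan as written is invalid.

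**What to change.** 1. Delete the skewness sentence in the SAP, 3C.8.1 and 4.4. State in section 3.3 that the distributional check at the end of data collection is descriptive and does not choose the H1 model.
2. Name one primary H1 model that does not need variance equal to mean: Poisson, log link, robust (sandwich) variance, one total count per offender, treatment as fixed effect, two-sided 5%. PROC GENMOD can fit this through a REPEATED statement. Give negative binomial as a sensitivity analysis. A fully defined negative binomial or random-effect model would also close the gap; the robust Poisson held error in every shape tested.
3. In the SAP, 3C.8.2 and 4.4, replace the random-effect sentence with that variance statement for the primary test. For the planned time-by-treatment analysis, define separately the intervals, the model and a procedure that fits it.
4. In Sample Size Determination (SAP, 3C.6.5, 4.4), state that 90% power at 119 per group holds only with Poisson variance, and show the power range above.
5. Add a log observed-time offset only if exposure time can be derived from data the trial already obtains, such as withdrawal dates. Section 3.2.A makes exposure relevant ("No additional data will be collected from participants who decide to withdraw"), but the documents do not provide for device installation or removal dates.

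Items 1 to 4 need no new data. The price is wider intervals and lower stated power for the 20% reduction if counts are overdispersed. Power for the 40% reduction would still be about 94% at variance/mean 5 with 127 per arm.
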